7.3 Study procedures

Questionnaires

After the eligibility check and obtaining informed consent, participants will receive a login code and a link to the study website by email. All questionnaires will be offered online using email notifications or text notifications. After enrolment, participants will be invited to fill out the baseline questionnaire (i.e., at month 0). Subsequently, a questionnaire will be offered to all participants every 6 months (i.e., at month 6, 12, 18 and 24), measuring risk behaviour over the past 6 months. Email reminders will be sent to the participants in case the questionnaire was not completed 1.5 week and 3 weeks after the first email notification was sent.

Run-in period

All participants will receive standard care during the run-in period of six months. HIV-positive MSM will receive standard care during biannual visits at their HIV treatment center, where routine blood testing, including liver enzymes, takes place every 6 months according to national guidelines.(64) Testing policies for HCV reinfection might differ per HIV treatment center; some centers might perform annual testing and others might only test for HCV RNA in the presence of elevated liver enzymes. In addition, the majority of HIV-positive MSM regularly visits the STI outpatient clinic of a Public Health Service for STI testing.

Standard care among HIV-negative MSM differs. HIV-negative MSM using PrEP will usually receive STI testing at an STI/PrEP/sexual health center. MSM participating in the PrEP projects will routinely visit the STI clinic of the Public Health Service of Amsterdam for PrEP monitoring including STI screening (syphilis, hepatitis B, hepatitis C, HIV, chlamydia and gonorrhoea). MSM enrolled in the PrEP projects at the Public Health Service of Amsterdam are currently being tested for HCV reinfection every 3 to 6 months. HIV-negative MSM not using PrEP are not routinely tested for HCV infection, unless they are notified by a HCV positive sex partner.

Intervention period

After randomization at month 6, participants will be referred to one of the three arms on the study website: (1) the behavioural intervention (see **Chapter 5.1**), (2) the testing intervention (see **Chapter 5.2**), or (3) the combined intervention (see **Chapter 5.3**). In addition to standard care as described above, participants will be offered the intervention(s) for 18 months (month 6-24).

After the end of the study

Additional HCV RNA blood testing will retrospectively be performed to test for HCV reinfection if: 1) the participant did not receive HCV RNA testing in the 6 months prior to the end of the study period, 2) there is a blood sample available for HCV RNA testing at the laboratory of the participating site and 3) the participant provided consent for retrospective HCV RNA testing in the informed consent form. These blood samples are collected during routine visits at the HIV treatment center or during visits at the STI/PreP/sexual health center. All study procedures are shown in **Table 1**.

Study procedures	Inclusion	Month 0	Month 6	Month 12	Month 18	Month 24	After the end of the study
Eligibility check	x						
Informed consent	x						
Questionnaire		x	x	x	x	x	
Online randomization			x				
Behavioural intervention			x	x	x		
Testing intervention			x	x	x		
Combined intervention			x	x	x		

HCV RNA testing in a stored blood sample*								X
---	--	--	--	--	--	--	--	---

* in case no HCV RNA test was performed in the last 6 months of the study period.

Table 1: Study procedures ICECREAM study

7.4 Withdrawal of individual subjects

Subjects can leave the study at any time for any reason if they wish to do so without any consequences. The investigator can decide to withdraw a subject from the study for urgent medical reasons.

7.5 Replacement of individual subjects after withdrawal

Individual subjects that chose to withdraw from the study will be replaced by other participants if recruitment is still ongoing.

8. SAFETY REPORTING

8.1 Temporary halt for reasons of subject safety

In accordance to section 10, subsection 4, of the WMO, the sponsor will suspend the study if there is sufficient ground that continuation of the study will jeopardise subject health or safety. The sponsor will notify the accredited METC without undue delay of a temporary halt including the reason for such an action. The study will be suspended pending a further positive decision by the accredited METC. The investigator will take care that all subjects are kept informed.

8.2 Data Safety Monitoring Board (DSMB) / Safety Committee

We determine that the associated risk and benefits are negligible for the participants included in this study. A data safety monitoring board was therefore deemed unnecessary.

9. STATISTICAL ANALYSIS

9.1 Primary study parameter(s)

The primary outcome is the proportion at risk of HCV infection (as determined by a HCV-MOSAIC score ≥ 2.0) during the run-in versus intervention periods. The score is calculated by summing up the beta-coefficients specific to six self-reported risk factors when present in the previous 6 months (see [Chapter 7.1.1](#)). The HCV-MOSAIC risk score has been previously validated for acute (primary) HCV-infection in HIV-positive MSM and the optimal cut-off to predict HCV positivity was defined at ≥ 2.0 .(65) In addition, we recently evaluated whether the risk score could also identify individuals at high-risk of HCV reinfection, showing comparable performance (The Area Under the ROC Curve = 0.76) to that of primary acute HCV-infection.(66)

The six items of the HCV-MOSAIC risk score will be obtained using the answers from the study questionnaire every six months. The proportion achieving the primary outcome will be summarized at month 6, 12, 18 and 24 visits within each study arm. The probability of the primary outcome will be compared between the run-in (month 6) and intervention periods (month 12, month 18, month 24) using a mixed-effect logistic regression model. In this model, each individual will serve as their own control and between-individual differences at baseline will be accounted for using a random-intercept. Pre versus post-intervention odds ratios (ORs) and their 95% confidence intervals (CI) will be estimated and stratified on study arm, allowing us to identify interventions with significant differences. No multivariable adjustments will be applied. Additional analysis will be conducted in which ORs between arms will be compared by including and testing an interaction term between period and arm in the model (two arms at a time, for a possible three comparisons). No *p*-value adjustments will be made for multiple comparisons to avoid unnecessary correction on the possibly underpowered test for interaction.(67)

Analyses will be performed by intention to treat (ITT) and per protocol (PP). Both analyses will only include individuals completing the lead-in phase (month-6). ITT analysis is defined by including all observations, while assuming that any individual lost to follow-up did not achieve the primary endpoint. PP analysis is defined by including all available observations, while excluding observations after an individual has been lost to follow-up. Subgroup analysis will also be conducted in order to determine whether individuals with certain characteristics are more likely to have a decrease in HCV-MOSAIC score.

9.2 Secondary study parameter(s)

Incidence rates of HCV reinfections and STIs will be calculated at the end of follow-up. Incidence of HCV reinfection will be examined during the lead-in and intervention periods of the RT. Considering few HCV reinfections are likely to occur, we intend to analyse differences in periods, along with associated risk-factors, using Bayesian exponential survival regression models with non to weakly informative *a priori* distributions.(68)

For all other secondary study parameters, continuous variables will be summarized using means or medians and categorical variables using counts and percentages at each study visit. Changes over time will be described for HCV related risk behaviour, disinfection behaviour and sexual wellbeing. We will use statistical regression methods specific to the endpoint (logistic for binary outcomes, linear for continuous variables), corrected for repeated measurements within individuals (using mixed-effect methods) to investigate changes between lead-in and intervention periods and associated determinants. Outcomes will also be compared across the 3 arms.

9.3 Other study parameters

Descriptive statistical analyses will be performed to describe study population characteristics, intervention-related outcomes (e.g. use of the services, acceptability and usability) and the number of (home-based) tests obtained and used from other sources.

9.4 Interim analysis

No study arms plan to be discontinued due to preliminary signals of ineffectiveness. No harmful effects are remotely expected during participation in the arms. Therefore, no interim analysis is planned.

9.5 Mathematical modelling

Using mathematical modelling and incorporating the outcomes of the RT, we will evaluate the impact of the RT interventions on reinfection incidence and onward transmission taking the increased uptake of DAA and the undiagnosed population into account. The impact of HCV awareness, early diagnosis and treatment on this HCV spread will be investigated. We will build on previous and ongoing modelling work: a deterministic mathematical model that simulates both HCV and HIV transmission dynamics among MSM simultaneously, which is currently being developed, and an individual based model for HCV and HIV transmission dynamics among people who use drugs.(11) Parameters will be derived from the ICECREAM study and from literature. Mathematical modelling will

be performed in collaboration with the Infectious Disease Dynamics Group at the University Medical Center Utrecht.

10. ETHICAL CONSIDERATIONS

10.1 Regulation statement

The study will be conducted according to the principles of the Declaration of Helsinki (Seventh revision, October 2013) and in accordance with the Medical Research Involving Human Subjects Act (WMO) of Dutch law.

10.2 Recruitment and consent

We will invite MSM aged 18 years or older with a history of a cured or spontaneously cleared HCV infection and in care at an HIV treatment center or using STI/PrEP related care to participate in the RT. Treating physicians and nurses at the study centers will propose the study to individuals meeting the inclusion criteria. Treating physicians include infectious disease specialists and doctors from the STI outpatient clinic and PrEP projects. Nurses include HIV nurse consultants/specialists and nurses from the STI outpatient clinic and PrEP projects. The HCV infection in the past will be confirmed by the treating physicians or nurses who enrol the participant by checking the laboratory results in the patient files. Information will be given both verbally and in a written information brochure. Adequate opportunity will be provided to the potential subject to ask questions. After written informed consent is obtained, the subjects will be included in the study. A copy of the signed informed consent form will be given to the participant. The informed consent forms will be retained at the participating site. A copy of the informed consent form will be sent to the Public Health Service of Amsterdam (coordinating center).

10.3 Benefits and risks assessment, group relatedness

In this study, only adults will be included. The questionnaires and interventions that will be offered in this study will not pose any other or additional risk than standard care. Participants will be exposed to five questionnaires, containing personal questions about sexual risk behaviour and drug use. Both the questionnaires and the interventions can make the participants more aware of their HCV risk, which could make participants feel at unease. However, we think that MSM who do not want to be confronted with their HCV risk behaviour and risk will not be interested in participating in this study.

A benefit of participating in the study might be a decreased risk of HCV infection and lower levels of risk behaviour, depending on the outcome of the study. Furthermore, the participants assigned to the testing or combined intervention will receive 4 free of charge

home-based tests, which might lead to more frequent, patient-initiated, testing and possibly earlier diagnosis of HCV infection and start of treatment. Another possible benefit could be that men can contribute to reducing the spread of HCV in the MSM community.

We classify this study as having a low chance of possible risk and a low degree of harm, leading to a negligible risk to participants.

10.4 Compensation for injury

The sponsor has a liability insurance which is in accordance with article 7 of the WMO. The reviewing committee of the AMC is of the opinion that there are no additional risks for the research subjects participating in this study, they therefore granted dispensation from the WMO subject insurance.

10.5 Incentives

No incentives will be provided to the participants.

11. ADMINISTRATIVE ASPECTS, MONITORING AND PUBLICATION

11.1 Handling and storage of data and documents

After obtaining informed consent, the treating physician/nurse will send the following details of the participant to the project leader at the Public Health Service of Amsterdam via Secure-email:

- Registration form:
 - First name and surname. Required for the linkage of the attached informed consent form to the participant.
 - Email address. Required for sending login data for the study website, email notifications and email reminders for the questionnaires and the intervention(s).
 - Telephone number. Required to contact the participants in case of HCV RNA positive test results.
 - Date of birth. Required to link reinfection data from the STI outpatient clinic to the participant.
 - If the participant is HIV-positive and is recruited at the Public Health Service of Amsterdam, HIV treatment center and physician/HIV nurse consultant will also be collected via the registration form. Required to link reinfection data from the HIV treatment center to the participant.
- A copy of the informed consent form. The informed consent form contains the subjects consent regarding linkage of data. The signed forms will be retained at the participating site. However, as the linkage will be coordinated by the Public Health Service of Amsterdam, a copy of the informed consent form will be required at the coordinating site.

It will be communicated both verbally and written (in the information brochure and the informed consent form) that the personal data mentioned above, will be transferred from the treating physician/nurse to the project leader at the Public Health Service of Amsterdam via Secure email.

The project leader registers the participant in het personal SQL database (database 1) and generates a random study number for each participant. The study number is communicated to the treating physician/nurse in the inclusion center by a reply email to the Secure-email mentioned above.

Data will be collected as follows:

- Self-reported clinical and behavioural data of participants will be collected by online questionnaires using LimeSurvey software.
- Data on the use of the services of the behavioural intervention will be collected from the study website, including the exposure to and intensity of use of each of the components of the online behavioural intervention (using log-data) if assigned to intervention I or III.
- Data on the number of free HCV home-based test(s) used and their test results will be collected from Castor EDC platform if assigned to intervention II or III.
- Data on HCV reinfection (HCV RNA test date(s), test results and HCV treatment) will be collected from laboratory and clinical files of the participating sites, and the Dutch HIV monitoring foundation (in Dutch: Stichting HIV Monitoring, SHM):
 - HIV treatment center: only for HIV-positive participants. Linkage will be performed using study number if the participant provided consent via the informed consent form. Linkage to SHM data will be through the HIV treatment centers using routine procedures.
 - STI/PrEP/sexual health center: for HIV-negative participants and HIV-positive participants (HIV-positive patients also visit the STI outpatient clinic at the Public Health Center of Amsterdam). Linkage will be performed using name and date of birth to link the STI data.
- Additional HCV RNA blood testing will retrospectively be performed to test for HCV reinfection if: 1) the participant did not receive HCV RNA testing in the 6 months prior to the end of the study period, 2) there is a blood sample available for HCV RNA testing at the laboratory of the participating site and 3) the participant provided consent for retrospective HCV RNA testing in the informed consent form. These blood samples are routinely collected during visits at the HIV treatment center or at the STI/PrEP/sexual health center every 3-6 months (see **Chapter 7.3**) and are retained at the laboratory for a minimum of 2 years according to law.

The data manager at the Public Health Service of Amsterdam will import the data from the questionnaires, the behavioural intervention, Castor EDC, HCV test results and clinical data into the Research SQL database (database 2).

The data of the participants will be stored in two separate databases: 1) containing study number and directly identifiable personal data (subject identification code list) and 2) containing study number and study data (e.g., sexual risk behaviour data). The subject

identification code list will be safeguarded by a key and will only be accessible by the project leader and data manager if necessary. A subject identification code list (database 1) will be used to link the data to the subject. This code list will be kept until 5 years after the end of the project. The DBS samples will be kept until 1 year after the end of the project. All other study data (database 2) will be stored for 15 years.

11.2 Amendments

Amendments are changes made to the research after a favourable opinion by the accredited METC has been given. All amendments will be notified to the METC that gave a favourable opinion. All substantial amendments will be notified to the METC and to the competent authority. Non-substantial amendments will not be notified to the accredited METC and the competent authority, but will be recorded and filed by the sponsor.

11.3 Annual progress report

The sponsor/investigator will submit a summary of the progress of the trial to the accredited METC once a year. Information will be provided on the date of inclusion of the first subject, numbers of subjects included and numbers of subjects that have completed the trial and amendments. We will not be able to trace serious adverse events/ serious adverse reactions as only one site visit is required at the start of the study and all further study procedures will take place online or at home. No harmful effects are remotely expected during participation.

11.4 Temporary halt and (prematurely) end of study report

The investigator/sponsor will notify the accredited METC of the end of the study within a period of 8 weeks. The end of the study is defined as completion of the final questionnaire by the last included subject. The sponsor will notify the METC immediately of a temporary halt of the study, including the reason of such an action. In case the study is ended prematurely, the sponsor will notify the accredited METC within 15 days, including the reasons for the premature termination. Within one year after the end of the study, the investigator/sponsor will submit a final study report with the results of the study, including any publications/abstracts of the study, to the accredited METC.

11.5 Public disclosure and publication policy

We intent to publish study outcomes in the most appropriate peer-reviewed scientific journals and at scientific conferences. Authorship will follow the guidelines defined by the International Committee of Medical Journal Editors. In addition, participants, their

community and relevant stakeholder will be informed in layman's terms about (the outcomes of) the study.

1. TRIAL SYNOPSIS

1.1. TRIAL OBJECTIVES

1.1.1. Primary objective

The primary objective is to investigate whether a behavioural and testing intervention, alone or in combination, has an effect on self-reported behaviours associated with hepatitis C virus (HCV) acquisition in men who have sex with men (MSM) with cured or spontaneously cleared HCV infection.

1.1.2. Secondary objectives

Secondary objectives are to evaluate the effect of a behavioural intervention and testing intervention, alone or in combination, on:

- HCV reinfection incidence
- Other HCV-related behaviours
- Sexually transmitted infection (STI) incidence
- Sexual wellbeing

1.2. TRIAL DESIGN

1.2.1. Study design and methods

This study is an international, multi-centre, phase 2, 3-arm, randomized trial (RT) comparing run-in and intervention periods to evaluate the effect of an online behavioural intervention, a home-based sampling for testing intervention, or both on self-reported behaviours associated with HCV acquisition. The first 6 months of the trial includes follow-up with no intervention (termed the “run-in” period) during which participants receive standard care. At month (M) 6, participants are randomly assigned, with an allocation ratio of 1:1:1, to one of the following three arms: (1) a targeted, online behavioural intervention; (2) a participant-initiated, home-based HCV-RNA self-sampling test service using dried blood spots (DBS); (3) consists of a combination of intervention I and II. Participants continue the intervention for 18 months (termed the “intervention” period) in addition to standard care. During both the run-in and intervention periods, five online questionnaires measuring risk behaviour over the past 6 months are administered (i.e., at M0, M6, M12, M18 and M24 of the study).

1.3. RANDOMISATION

Randomisation takes place via an online, centralized system. Lists of randomly permuted blocks assigning six interventions (i.e., two from each of the three arms) are generated. Research staff do not have access to the randomisation sequence nor do they know the arms randomly assigned to individuals before a given participant is recruited.

1.4. SAMPLE SIZE

We aim to have a minimum of 78 individuals per arm (total of 234) who complete at least one study questionnaire during the intervention period. Assuming a maximum drop-out rate of 5% during the run-in period, 246 participants in total are needed to be enrolled. We simulated power under varying proportions at risk of HCV infection during the run-in period and absolute risk reduction during the intervention. With a sample size of 78 in each arm, we would have 80% power to demonstrate a statistically significant difference, at a type 1 error of 0.05, of a >22% reduction in the primary endpoint from a 60% proportion at risk of HCV infection during the run-in period.

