4.4 Sample size calculation

We aim to have a minimum of 78 MSM per arm (total: 234). Assuming a drop-out rate of a maximum 5% in the run-in period (based on our experience with ongoing studies), we aim to enrol 246 MSM in total (see [Figure 1](#)). As we have no initial data on the effects of our interventions, we simulated power under varying conditions of at risk behaviour during the run-in period and absolute risk reduction during the intervention. With a sample size of 78 in each arm, we would have 80% power to demonstrate a statistically significant difference, at a type 1 error of 0.05, of a >22% reduction in the primary end-point from a 60% baseline prevalence of MSM identified as at risk (HCV-MOSAIC score ≥ 2.0 , see [Chapter 9.1](#)). When

testing for differences in reduction of the primary end-point between two intervention arms (**Chapter 9.1**), while additionally assuming a 10% reduction in the comparator arm, we would have 80% power to demonstrate a statistically significant difference if a reduction of 0.43 was observed in the other intervention arm.

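### SAP 1.4 counts its 78 per arm after randomisation but allows only for loss before it, and states 80% power without the loss assumption and ITT rule on which that figure depends

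*SAP*

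**What the plan says.** - **SAP 1.4** defines the target as a "minimum of 78 individuals per arm (total of 234) who complete at least one study questionnaire during the intervention period". It then continues: "Assuming a maximum drop-out rate of 5% during the run-in period, 246 participants in total are needed to be enrolled".
- **Protocol 4.4** has the same 78, 234 and 246 but attaches no questionnaire condition: "We aim to have a minimum of 78 MSM per arm (total: 234"). Protocol 9.1 says of ITT and PP: "Both analyses will only include individuals completing the lead-in phase (month-6"). That set fits a count of men who reach randomisation.
- **Power.** Both documents claim 80% power at a type 1 error of 0.05 for a difference, in the protocol's words, "of a >22% reduction in the primary end-point from a 60% baseline prevalence of MSM identified as at risk". The only simulation conditions they name are the run-in proportion and the absolute reduction.
- **Contrast.** Under protocol 9.1 the outcome is "compared between the run-in (month 6) and intervention periods (month 12, month 18, month 24) using a mixed-effect logistic regression model". SAP 2.2.2 compares the run-in (M0, M6) with each later visit separately. SAP 3.4.1 describes the comparison by period.
- **Lost men.** Under SAP 2.1.1, ITT treats a man lost to follow-up as at risk. PP drops his observations after loss and also removes men who did not receive their assigned intervention. SAP 2.1 allows the Scientific Committee to consider excluding some men, including those who withdraw consent.
- **Replacement.** Protocol 7.5 says withdrawn men "will be replaced by other participants if recruitment is still ongoing".

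**The concern.** The SAP's target is a count that can be made only after randomisation, but the enrolment figure is inflated only for loss before it. The SAP attaches a condition that the text of protocol 4.4 does not have, and keeps the same numbers. The SAP 3.1.1 flowchart lists men randomised and men who completed every visit. It does not list men with at least one later questionnaire, so it would not show whether the 78 was reached.

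The power statement matters more. Protocol section 3 makes a significant within-arm decrease the pilot's test. ITT keeps a man with no later questionnaire and scores him as at risk, so loss dilutes the apparent effect rather than reducing the sample. If ITT shows no significant decrease, readers will need to know whether that could come from the coding of lost men. An 80% figure with no stated loss rate or rule for lost men cannot tell them.

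**Working it through.** **1. The enrolment figure.** Inputs from SAP 1.4: 246 enrolled, 5% run-in loss, three arms.

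- 246 × 0.95 = 233.7, or 77.9 per arm. This is the number randomised at M6.
- The documents give no rate for men randomised who return none of M12, M18 and M24. Assume 2%, 5% or 10%:
  - 233.7 × 0.98 = 229.0, or 76.3 per arm
  - 233.7 × 0.95 = 222.0, or 74.0 per arm
  - 233.7 × 0.90 = 210.3, or 70.1 per arm
- With no run-in loss at all, non-response up to 1 − 234/246 = 4.9% would still meet 234.

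**2. The stated power.** Take p1 = 0.60, p2 = 0.38 (a 22-point absolute drop), n = 78, and α = 0.05 two-sided (sidedness is not stated), as two independent samples.

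- Pooled SE under the null: √(2 × 0.49 × 0.51/78) = 0.0800
- SE under the alternative: √((0.60 × 0.40 + 0.38 × 0.62)/78) = 0.0781
- Power: Φ((0.22 − 1.96 × 0.0800)/0.0781) = 0.79. With the unpooled SE throughout it is 0.80.

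This matches the stated 80%. A relative 22% reduction (60% to 46.8%) would give only 0.38, so the effect is absolute. The same pooled formula gives 0.77 at n = 74 and 0.75 at n = 70, so the shortfall in step 1 matters little by itself.

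**3. The ITT rule.** If a share L is lost by a visit, independently of outcome, the ITT proportion at risk there is 0.38(1 − L) + L. The apparent drop is therefore 0.60 − 0.38(1 − L) − L = 0.22 − 0.62L:

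- L = 5%: 18.9 points
- L = 10%: 15.8 points
- L = 15%: 12.7 points

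**4. Power under an own-control model.** This is a simulated random-intercept logistic model with n = 78 and a true 22-point drop, using a likelihood-ratio test at 0.05. There were 600 replicates per cell (Monte Carlo SE up to 0.021). Random-intercept SDs were 1.12, 1.79 and 2.70, for within-person correlations of 0.2, 0.35 and 0.5. Loss was independent of outcome, and ITT set lost visits to at risk. Loss rates, timing and correlations are assumptions.

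| Lost by M24 | ITT, M0+M6 v M24 (SAP 2.2.2) | ITT, M6 v M12–M24 (protocol 9.1), all lost before M12 | Same, loss spread evenly over visits |
|---|---|---|---|
| 0% | 0.96–1.00 | 0.96–1.00 | 0.96–1.00 |
| 5% | 0.87–0.97 | 0.89–0.98 | 0.94–0.99 |
| 10% | 0.72–0.85 | 0.78–0.90 | 0.85–0.95 |
| 15% | 0.54–0.72 | 0.61–0.74 | 0.76–0.90 |

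A simpler paired contrast shows the same pattern: about 0.68–0.83 at M24 with 10% lost, and a low end of about 0.73 in the bottom right cell.

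**5. Detectable reduction.** For 80% power at 0, 5, 10 and 15% loss (correlation 0.2 and 0.5):

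- ITT at M24: 14–17, 17–20, 20–24 and 24–27 points
- ITT period contrast with spread loss: 13–16, 15–18, 17–20 and 20–23 points

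**The case against.** The strongest reply is that nothing is miscalculated. 246 less 5% is 234, 80% power reproduces, 78 is an aim and 5% is a maximum. This stands. The fault is that the SAP's definition of the 78 does not match its allowance, and that the power figure lacks its conditions. The size shortfall alone is minor.

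A reader might infer that 22 points is generally optimistic for ITT from about 10% loss. The calculations do not support that. The below-80% results arise when M24 is tested as a separate visit or when all loss comes before M12. With loss spread over visits, the period contrast detects 17–20 points at 10% loss, so 22 remains conservative there.

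A reader might also infer that the simulation ignored loss. The documents do not say how it was run, and a numerical match to independent samples does not settle it. Figure 1 of the protocol and the published protocol cited by the SAP were not available to check.

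Other limits also stand:

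- The ITT figures score every lost man as at risk, although SAP 2.1 may exclude men who withdrew consent.
- Simulating loss alone says little about PP, which also removes men who did not receive their assigned intervention.
- SAP 3.1.4 and 3.1.5 report visits conducted and last visit before discontinuation, so attrition is partly visible. They do not give the count that SAP 1.4 uses.
- Defining the 78 as men randomised is an easier target. That is acceptable only if the expected number of responders is stated beside it.

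**Conclusion.** The point holds, at minor to moderate weight. At the planned run-in loss, SAP 1.4 does not deliver its own stated size unless every randomised man returns a later questionnaire. Replacement helps only with withdrawals while recruitment is open. The direct cost in power is one or two points at 5% non-response and about four at 10%.

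The 80% figure does not describe the planned analyses. It is conservative for the own-control model with no or little loss. Under the ITT rule it can be too high from about 10% loss for M24 alone or for early loss. For the period contrast with spread loss, power is at or above about 0.85 at 10% and about 0.73–0.90 at 15%. These ranges rest on assumed loss, timing, correlation of 0.2–0.5 and loss unrelated to outcome. The only loss rate in the documents is the 5% run-in maximum. The material does not support calling the trial underpowered or asking for more participants.

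**What to change.** - **SAP 1.4.** Define the 78 as men randomised, which is consistent with protocol 4.4 and the month-6 analysis set in protocol 9.1. State the expected number per arm with at least one later questionnaire at a named assumed loss, for example 74 at 5%.
- **SAP 3.1.1.** Add that count, per arm, to the flowchart.
- **Power.** Rerun the simulation under the planned random-intercept model, separately for ITT and PP. ITT should include the lost-equals-at-risk rule and the possible exclusions in SAP 2.1. PP should include removal of men who did not receive their assigned intervention.
- **Reporting.** In SAP 1.4 and protocol 4.4, restate the detectable reduction in percentage points with the correlation, the contrast (period or single visit), the loss rate and the timing of loss. Let the rerun decide whether 22 points is described as conservative or optimistic.

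The cost is one rerun, some rewording and one flowchart line, with no extra enrolment. The stated ITT figure may turn out less favourable than 22 points.
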